15.7 Prompt Reporting of SAEs to Sponsor

The sponsor has requirements for reporting serious adverse events to regulatory agencies for a drug under clinical investigation. The sponsor must be notified within 24 hours of discovery if the investigator determines that an adverse event meets the protocol definition of an SAE.

All SAEs occurring from the time of IUS insertion through study exit require immediate reporting to the sponsor. Investigators should not wait to receive additional information to fully document the event prior to notifying the sponsor but should provide as much relevant information as immediately available. Further details of the event can be provided as they become available. The procedures for reporting SAEs are as follows:

- Complete the "Serious Adverse Event Report" form;
- Submit the completed form to sponsor;
- Also submit copies of hospital case reports, autopsy reports, and other documents when requested and applicable;
- The sponsor may request additional information from the investigator to ensure the timely completion of accurate safety reports;
- Any fatal or life-threatening events should also be reported immediately by telephone to sponsor;
- The SAE report should be completed as thoroughly as possible and signed by the investigator before transmittal to sponsor. It is very important that the Investigator

- provides an assessment of the causal relationship between the event and the study drug at the time of the initial report; and
- The investigator, or responsible person according to local requirements, must comply with the applicable local regulatory requirements concerning the reporting of SAEs to regulatory authorities and the IRB.

15.8 Clinical Laboratory Abnormalities and Other Abnormal Assessments as Adverse Events and Serious Adverse Events

Abnormal laboratory findings (e.g., clinical chemistry, hematology) or other abnormal assessments (e.g., electrocardiogram, X-rays, vital signs) per se are not reported as AEs. However, abnormal findings that are deemed clinically significant (i.e., associated with signs and/or symptoms or requiring therapeutic intervention) must be recorded as AEs if they meet the definition of an adverse event (and recorded as an SAE if they meet the criteria of being serious) as described previously. Clinically significant abnormal laboratory or other abnormal findings that are detected after study drug placement or that are present at baseline and worsen following placement of IUS are included as AEs (or SAEs if serious).

The investigator should exercise his or her medical judgment in deciding whether an abnormal laboratory finding, or other abnormal assessment is clinically significant. A clinically significant laboratory abnormality in the absence of clinical symptoms may also jeopardize the subject and may require intervention to prevent immediate consequences (e.g., a markedly high serum potassium concentration may not be accompanied by arrhythmia yet be of a magnitude to require potassium-binding resin administration to prevent such sequelae). Subjects should undergo repeat testing of clinically significant abnormal laboratory findings as soon as they are recognized.

15.9 Documenting Adverse Events

Any AE occurring from the time of informed consent/assent through VeraCept removal or expulsion must be documented in the subject's study records and on the AE eCRF. SAEs that occur during the study must be documented in the subject's study record, on the AE eCRF and on the SAE report as appropriate.

The investigator's assessment of causality, severity and status of the adverse event must be documented. When a causality assessment is provided for a serious adverse event, it is important to include a rationale for the assessment so that a better understanding of the reported event can be compiled. The rationale should be accompanied by all available supporting evidence, including relevant laboratory tests, histopathology evaluations and the results of other diagnostic procedures. The investigator's rationale with supporting evidence is valuable when sponsor performs a cumulative analysis of similar events.

15.10 Follow-up of Adverse Events and Serious Adverse Events

All AEs and SAEs must be followed until resolution, the condition stabilizes, 30 days post study drug removal or expulsion, or the subject dies or is lost to follow-up (including withdrawal of consent/assent), whichever occurs first. The investigator is responsible for

ensuring that follow-up includes any supplemental investigations as may be indicated to elucidate as completely as practical the nature and/or causality of the AE/SAE. This may include additional laboratory tests or investigations, histopathologic examinations, or consultation with other health care professionals. Follow-up information should be submitted to the sponsor in a timely many as the information is obtained.

15.11 Clarification in Reporting of Deaths

All subject deaths (regardless of relationship to study drug) should be reported that occur from the beginning of study drug placement through Study Exit. The information should be recorded on the Subject Death form and the SAE report.

15.12 Post-Study Treatment Reporting Requirements

For all enrolled subjects, all AEs and SAEs, regardless of cause or relationship, that occur from the beginning of study drug placement through VeraCept removal or expulsion require reporting to the sponsor. In addition, if the investigator learns of any SAE at any time after a subject has had the study drug removed, and such event seems reasonably related to study drug, the investigator should immediately notify the sponsor.

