Although pregnancy is not considered an adverse event, there is a possible risk of becoming pregnant while using VeraCept.

In addition to the above known risks, the following additional adverse events have been reported in association with Paragard T380A IUS(16). Adverse events associated with the Paragard T380A IUS may be relevant because it is also a copper-based contraceptive. The severity or frequency of any of the following events, should they occur, is not expected to be any different with the use of VeraCept. These events are not in order of severity or frequency.

- Risks with Intrauterine Pregnancy: septic abortion, premature delivery, sepsis, septic shock and death if pregnancy occurs.
- Sepsis: Group A streptococcal infection has been reported; strict aseptic technique is essential during insertion

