- 9. Contact subject (e.g., via phone, email, etc.). Starting at Week 17 from day of VeraCept insertion.
- 10. See Appendix 2 for the IUD Insertion Subject Numeric Pain Rating Scale
- 11. See Appendix 3 for the IUD Removal Subject Numeric Pain Rating Scale
- 12. Upon receipt of informed consent and assent, if applicable, contact the IWRS to register the subject, initiate the subject's screening diary and obtain a subject number
- 13. Contact the IWRS prior to insertion to obtain an enrollment number, the IUS dispensation assignment, and initiate the enrollment diary. If an IUS insertion is a failure, contact the IWRS to record the IUS insertion failure and to obtain a second IUS dispensation assignment or to discontinue the subject
- 14. See Appendix 4 for Pre-Removal Planning Timing
- 15. See Appendix 5 for Removal Instructions
- 16. An additional contact will be performed 30 days post-removal or expulsion for any AEs that were ongoing at the time of VeraCept removal. If the date of expulsion is unknown the additional contact will be performed 30 days after the date of expulsion discovery.
- 17. Subjects completing at least 6 years (72 months) of study will complete a Subject Satisfaction Survey at the Exit Visit.

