15.1 Definition of a Serious Adverse Event

A serious adverse event (SAE) is any adverse event occurring within the timelines specified in the protocol that results in any of the following outcomes:

- Death;
- Life-threatening situation (subject is at immediate risk of death);
- Inpatient hospitalization or prolongation of existing hospitalization;
- Persistent or significant disability/incapacity;
- Congenital anomaly/birth defect in the offspring of a subject who received study drug; or
- Important medical events that may not result in death, be immediately life-threatening, or require hospitalization, may be considered an SAE when, based upon appropriate medical judgment, they may jeopardize the subject and may require medical or surgical intervention to prevent one of the outcomes listed in this definition. Examples of serious adverse events include but are not limited to: intensive treatment in an emergency room, hospitalization for any reason, and extensive treatment at home for an adverse event. An ectopic pregnancy is considered a serious adverse event.

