15.2 Definition of an Adverse Event

An adverse event is any untoward medical occurrence in a clinical investigation subject administered an investigational product and which does not necessarily have to have a causal relationship with this treatment. An AE can, therefore, be any unfavorable and unintended sign (that could include a clinically significant abnormal laboratory finding), symptom, or disease temporally associated with the use of a medicinal product, whether or not considered related to the medicinal product.

Any AE (i.e., a new event or an exacerbation of a pre-existing condition) with an onset from the day of informed consent/assent through VeraCept removal or expulsion should be recorded as an AE on the eCRF. An event that is discovered during the screening visit that clearly started or was acquired prior to obtaining informed consent (e.g., positive cervical infection test, positive cervical pathology) should be recorded as medical history and not as an AE. All AEs must be recorded regardless of the severity or relationship to study drug. It is important that investigators also report all AEs that result in expulsion or removal of the investigational product being studied, whether serious or non-serious.

Pregnancy is an outcome, and not an AE in this study.

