15.4.1 Clarification of Adverse Events Related to Study Procedures

Any untoward event that occurs from the time of informed consent/assent, including the study drug placement procedure until completion of placement, or from the beginning of the removal procedure until the completion of removal, will be reported as an AE. The AE

should be recorded on the AE eCRF with a causality assessment of "related to study drug placement procedure." If the AE also meets the criteria for an SAE, an SAE report should be completed and submitted to the sponsor.

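### No step in the protocol actively collects adverse events that begin after device removal or expulsion, and its sections disagree on where SAE reporting ends

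*Protocol*

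**What the plan says.** **Routine recording.** Protocol section 15.2 covers any AE "with an onset from the day of informed consent/assent through VeraCept removal or expulsion should be recorded as an AE on the eCRF". Section 15.9 uses the same limits. Section 15.12 covers AEs and SAEs of any cause that "occur from the beginning of study drug placement through VeraCept removal or expulsion require reporting to the sponsor". Its next sentence adds that an SAE the investigator learns of at any later time must be notified if it seems reasonably related to the study drug.

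**Removal procedure.** Section 15.4.1 covers untoward events from consent through placement "or from the beginning of the removal procedure until the completion of removal, will be reported as an AE".

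**SAEs and deaths.** Section 15.7 states: "All SAEs occurring from the time of IUS insertion through study exit require immediate reporting to the sponsor". Section 15.11 also takes death reporting to study exit. Section 15.1 ties the SAE definition to the protocol's own timelines, and its list includes "Congenital anomaly/birth defect in the offspring of a subject who received study drug".

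**After removal.** Section 15.10 states: "All AEs and SAEs must be followed until resolution, the condition stabilizes, 30 days post study drug removal or expulsion", or until death or loss to follow-up, whichever is first. Table 1, footnote 16 states: "An additional contact will be performed 30 days post-removal or expulsion for any AEs that were ongoing at the time of VeraCept removal". Section 12.7 and Table 1, footnote 4 require a home pregnancy test 17 days after removal or exit, with a call to obtain the result.

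**Pregnancy.** Exposed pregnancies are followed to at least 6 weeks after delivery. Section 18 has the clinical outcome recorded and infant abnormalities reported. In a first-trimester intrauterine pregnancy the device is to be removed if the threads are visible; if they are not accessible it stays until delivery. Section 6.2 carries over from another copper device the risks of "septic abortion, premature delivery, sepsis, septic shock and death if pregnancy occurs". Section 20.1 counts a conception up to 7 days after removal or expulsion as on-treatment.

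**The concern.** Some of the risks that the protocol names can begin after the device is out. Pelvic infection and bleeding can follow a removal that needed instruments in the uterine cavity, dilation or hysteroscopy, all of which Appendix 5 contemplates. Septic abortion and premature delivery can follow the removal of a device early in pregnancy. If routine recording stops at removal, such events reach the safety tables only when someone volunteers them.

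Pelvic infection, AEs and SAEs are secondary safety endpoints, and the trial has no comparator against which incomplete capture would cancel out. Capture also becomes uneven: whether the same maternal complication is routinely recorded depends on whether the device had been removed, which under section 18 depends on the threads. Finally, sites cannot apply one rule when two sections end SAE reporting at different points.

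**Working it through.** No planned figure is in dispute, so the main check is to set the windows side by side.

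| Section | Events | Start | End |
|---|---|---|---|
| 15.2, 15.9 | AEs | consent | removal or expulsion |
| 15.4.1 | procedure events | consent | completion of removal |
| 15.7 | SAEs | insertion | study exit |
| 15.11 | deaths | placement | study exit |
| 15.12, first sentence | AEs and SAEs, any cause | placement | removal or expulsion |
| 15.12, second sentence | related SAEs learned of | after removal | none |
| 15.10 | follow-up of events | – | 30 days after removal or expulsion at latest |
| SAP 4.1.10.1 | treatment-emergent AEs | first treatment date | not stated |

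**Step 1: do the ends agree?** No. Section 12.7 places removal at the exit visit, so study exit and removal usually coincide and 15.7 then adds little. Study exit is not defined for a woman in pregnancy or fertility follow-up, where the two can differ. The starts differ as well.

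**Step 2: which contact would find a new event?** The 30-day contact is triggered only by an AE already ongoing. The day-17 call has no stated AE question. In Table 1 the contacts for women desiring pregnancy carry no AE mark. No scheduled contact asks about events that began after removal.

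**Step 3: trace cases through the rules.**
- A vasovagal reaction during removal is an AE under 15.4.1.
- A non-serious infection that begins days after removal falls in no window and triggers no contact. If it is serious, it depends on the second sentence of 15.12.
- Take a maternal complication of an exposed pregnancy. With the device still in place, it lies inside the window of 15.2 and 15.12. After first-trimester removal it lies outside. It can then be recorded as a clinical outcome under section 18, or as a related SAE, but not through routine collection.
- A pregnancy conceived in the 7 days after removal lies wholly outside the routine window, although it is on-treatment.

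**Step 4: illustrate the unevenness.** Let G be the days from conception to delivery and r the days from conception to removal. Follow-up lasts G + 42 days (6 weeks after delivery). The share after the routine window closes is (G + 42 − r)/(G + 42). G is an assumption: 266 days, range 224 to 280. The removal times are also assumed.

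| Device history | G = 266 | G = 224 to 280 |
|---|---|---|
| Removed 3 weeks after conception (r = 21) | 287/308 = 93% | 92% to 93% |
| Removed 11 weeks after conception (r = 77) | 231/308 = 75% | 71% to 76% |
| Conception after removal (r set to 0) | 308/308 = 100% | 100% |
| Left until delivery (r = G) | 42/308 = 14% | 13% to 16% |

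These are shares of follow-up time in pregnancies that reach delivery at G, not shares of complications.

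**The case against.** The safety net is wider than the sentence quoted from 15.12 suggests, and four stronger readings fail.

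- **That removal complications are lost.** Section 15.4.1 captures events during removal, and SAP 4.12.1 and 4.12.2 plan summaries by relation to the removal procedure. Appendix 5 names pain, bleeding, vasovagal reactions and seizure, mostly events of the procedure itself. Section 6.2 lists pelvic infection as an event of device use, so its link to removal is an inference.
- **That SAE collection closes at removal.** The second sentence of 15.12 has no time limit, section 14 provides for medication given for reportable SAEs after removal, and 15.7 runs to study exit. The SAP's open-ended definition would not cut a late SAE from the tables.
- **That ectopic counts are biased down.** Ectopic pregnancy is a separate endpoint, an SAE by definition and a SAP summary item. The day-17 test looks for late conceptions, and section 18 requires immediate reporting. The documents do not show a bias.
- **That most complications of exposed pregnancies are lost, or that their number can be given.** One could divide the planned 54,000 to 65,000 cycles by 13 (4,154 to 5,000 woman-years) and apply the Phase 2 Pearl Index of 0.73 per 100 (95% CI 0.09 to 2.65). That gives 30 to 37 pregnancies, range about 4 to 133. It counts pregnancies, not missed events. It also applies a rate from the evaluable-for-pregnancy population, based on two pregnancies, to all cycles. No complication rate is given, nor how often the device would be removed.

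Section 18 also points to pregnancy reporting guidelines in the Study Reference Manual, which are not among these documents, and the version 7.0 history shows that AE timelines were revised deliberately.

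All of this limits the claim. It does not supply an active query for new events after removal, a route for non-serious ones, or an agreed end to SAE reporting. Recording a clinical outcome is also not the same as entering a maternal complication in the AE or SAE data.

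**Conclusion.** The point holds as a gap in active collection and an inconsistency between sections. After removal or expulsion, new non-serious AEs have no collection route. SAEs judged unrelated fall outside 15.12. Related SAEs are covered, but passively. Maternal complications of exposed pregnancies are inside or outside routine collection according to whether the device was removed, although the women remain under follow-up with outcome and infant abnormalities recorded.

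The size cannot be stated as a number of events. The only quantity available is follow-up time: 75% to 93% outside the window after removal at 11 or 3 weeks, against 14% with the device left until delivery, on an assumed 266 days and assumed removal times. The conclusion also assumes that the Study Reference Manual adds no AE query of its own. It concerns the safety endpoints, not the Pearl Index calculation. The protocol should be amended on this point.

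**What to change.** 1. Give sections 15.2, 15.7, 15.9, 15.11 and 15.12 one stated window that runs through the day-17 call already required after removal or exit, and add a scripted question on new events to that call. Define study exit for women in pregnancy or fertility follow-up.
2. Extend the 30-day contact to AEs that began after removal or expulsion.
3. For on-treatment or device-exposed pregnancies, record maternal and infant SAEs through the existing follow-up to 6 weeks after delivery, whatever the removal date, and exempt them from the 30-day limit in 15.10.
4. State in the SAP that these events enter the AE, SAE and special-interest tables, and give the treatment-emergent definition a matching end.

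The cost is protocol and SAP wording, one question on an existing call and a few more 30-day calls. Pregnancy follow-up contacts already exist. AE counts may rise slightly. None of this changes clinical management. Day 17 is proposed because the call is already scheduled; no figure in the documents singles it out, so another common end would also remove the inconsistency if a contact supports it.

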15.13 IUS or Inserter Malfunction

Should the IUS or its inserter not perform mechanically as expected, the sponsor should be informed. Details of the malfunction will be collected, and the sponsor will determine if the IUS and/or inserter should be returned to the study sponsor for assessment.

16 PROTOCOL VIOLATIONS AND DEVIATIONS

Except in the event of a medical emergency or where it is necessary to protect the safety, rights or welfare of the study subject, any changes to the protocol will require written approval of Sebela or designee. Violations or deviations from the Clinical Investigational Plan to protect the health and safety of the subject will be reported to the IRB and as required by local regulations. All protocol violations or deviations will be recorded, tracked and reviewed periodically by Sebela and its designee, according to the process established prior to first patient enrolled. A protocol violation or deviation may be requested in advance of implementation and will be reviewed for approval by Sebela or its designee, or a violations/deviation may be identified after the fact, by the investigator, Sebela, or the monitoring staff. Investigators will be asked to provide an explanation for all violations and deviations identified. Sebela, or designee, will be responsible for analyzing deviations and may implement corrective actions as necessary.

17 SUBJECT CONFIDENTIALITY

At all times throughout this study, all parties shall strictly observe the confidentiality of subject's health information. All data shall be secured against unauthorized access. Each subject participating in this study will have consented/assented to allow access to her data, as described during the informed consent process and documented in the signed informed consent/assent form. Each subject will also sign an Authorization for Release of Protected

Health Information (PHI) form granting Sebela and its designees access to her medical records, should she receive medical care from non-study sites where she gets care (e.g., emergency room, urgent care, etc.). Each subject will be assigned a unique identifier. All eCRFs will be tracked, evaluated, and stored using only this unique identifier. HIPAA guidelines and regulations will be followed.

The investigator will maintain a confidential study subject list identifying all enrolled subjects. This list will contain the assigned study subject's unique identifier and name. The investigator bears responsibility for keeping this list confidential. This list will not be provided to the study sponsor and is only to be used at the study center.

Monitors and auditors will have access to the study subject list and other personally identifying information of study subjects to ensure that data reported in the eCRFs corresponds to the person who signed the consent/assent form and the information contained in the original source documents. Such personal identifying information may include, but not limited to, the subject's name, address, date of birth, gender, race, and medical record number.

In an effort to protect subject confidentiality, any source documents copied for monitoring purposes by the sponsor or designee will be identified using the subject's assigned unique identifier and personal identifying data will be obscured.

